Total Time				55 Min	67 Min	61 Min	117 Min	106 Min

Primary Outcome Measures. The primary outcome measures include the total score from the Clinician Administered PTSD Scale (CAPS)⁶⁵ and the total score from the PTSD Checklist (PCL).⁶⁶ The CAPS is considered the “gold standard” diagnostic tool for PTSD assessment by the National Center for PTSD and has been extensively used and validated in clinical trials.^{68,69} The CAPS is a semi-structured clinician interview that measures PTSD diagnostic status and symptom severity consistent with the Diagnostic and Statistical Manual of Mental Disorders (5th ed.).⁶⁷ The CAPS yields both continuous and dichotomous scores for current PTSD symptoms. PTSD self-reported symptom severity will be assessed with the PTSD Checklist, a 20-item self-report measure of the DSM-5 symptoms of PTSD used as a measure of change in PTSD symptoms as a function of treatment. The PCL has demonstrated sensitivity and specificity >70%.^{66, 69, 70} The DSM-5 versions of these measures are not yet normed but should be available for use in this study.

PTSD-Specific Symptoms: The Medical Outcomes Study 12-item Sleep Scale (MOS) will assess **sleep quality** (sleep disturbance, adequacy of sleep, and sleep quantity) and has demonstrated good psychometric properties.⁷⁴ **Anger** will be assessed by the PROMIS Item Bank v. 1.1 – Emotional Distress - Anger - Short Form 5a. PROMIS stands for the NIH Patient Reported Outcome Measurement Information System which provides questions to produce numeric values which indicate patients' state of wellbeing or suffering as well as their ability or lack of ability to function that have been psychometrically validated..

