Data analysis: Baseline characteristics of the RELIEVE sample. To evaluate representativeness, we will compare enrollees and those who decline enrollment on baseline characteristics (socio-demographic variables, psychiatric comorbidity, and current and prior PTSD treatments). Any differences will be considered when interpreting results of subsequent analyses. We will also examine differences in baseline characteristics between patients who remain in the study and those who dropout. The linear mixed modeling approach (see next section) will ensure that all available data are used for subjects who have missing data. The models will also incorporate dropout status to adjust for follow-up missing data pattern. All participants will have baseline data. The possible missing data patterns will be (1) missing 4 month, not 7 month, (2) missing 7 month, not 4 month, (3) missing both 4 and 7 months, and (4) complete data.

Main analysis of the primary outcome. Our main analysis will use the ANCOVA (analysis of covariance) approach to linear mixed modeling of repeated measures in which the baseline measure of the relevant outcome scores (i.e., CAPS or PCL) is adjusted as a covariate in the model.⁸⁵ The model for CAPS will be adjusted for baseline CAPS score. The model for PCL, a continuous measure with a possible range of 17-85, will be adjusted for baseline PCL score. The CAPS and PCL are measured at every time point (baseline, 8 weeks, 4 months, 7 months) except the CAPS is not administered at 6 weeks in order to reduce participant burden, since the CAPS and PCL are highly correlated. We plan an intent-to-treat analysis with the primary endpoint at 4 months and evaluation of “early” response at 8 weeks and “sustained” response at 7 months (3 months post-intervention). The models will simultaneously incorporate three post-baseline measures (8 weeks ([PCL only], 4 months, and 7 months) of the relevant response variable. The main predictors will be group (treatment arm), time (categorical with indicator variables to avoid restrictive assumption of linearity over time), and their interaction. A random intercept will be used to adjust for the potential clustering effect for patients in

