a specific yoga group. And a subject-specific random intercept (nested within the group effect) will accommodate the correlation among repeated measurements from the same patient. Aim 1 will involve testing intervention effects by using the appropriate contrast from the model to test the difference in CAPS score and PCL score between the two treatment arms at 8 weeks (early response), 4 months (the primary end point which occurs immediately post intervention), and 7 months (sustained effect of intervention). Descriptive statistics including adjusted means, SD, and effect sizes (differences between two arms on adjusted means divided by pooled SD) will be reported for outcomes at each time point. Variables that are either known, or shown with our data, to be significantly correlated to the outcomes, will be considered as covariates, irrespective of their degree of baseline imbalance between randomized groups (e.g., combat vs. con-combat PTSD, baseline credibility score, and mTBI).

Secondary analysis of primary outcome. For the CAPS and PCL total scores, we will also report a clinically relevant descriptive statistic in which we define the patients with more than 30% reduction from baseline as “responders.” We will then compare the probability of responders between treatment arms using a generalized linear mixed model with a logit link. The responding status of each patient at 8 weeks (for PCL only), 4 months and 7 months will be used as the outcome variables. Main predictors are group (treatment arm), time (8 weeks for PCL only, 4 months and 7 months) and their interaction. A significant coefficient of group indicates a significant odds ratio of being a responder between the two arms.

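### The responder model contains a group-by-time interaction but is judged on the group coefficient alone, so the odds ratio tested depends on an unstated time coding and can fall at different visits for PCL and CAPS

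*Combined protocol and SAP*

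**What the plan says.** All of this is in section 8.0 unless noted.

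- **Responder model (Secondary analysis of primary outcome).** A responder has more than a 30% fall from baseline in CAPS or PCL total score. The arms are compared on this status, over the follow-up visits, with a generalized linear mixed model with a logit link. Its terms are listed as follows: "Main predictors are group (treatment arm), time (8 weeks for PCL only, 4 months and 7 months) and their interaction". PCL therefore enters at three visits and CAPS at two.
- **How it is read.** The one rule stated is "A significant coefficient of group indicates a significant odds ratio of being a responder between the two arms". The paragraph gives no time coding, reference visit, visit-specific contrast or joint test.
- **Continuous scores (Main analysis of the primary outcome).** Time is specified as "time (categorical with indicator variables to avoid restrictive assumption of linearity over time"). Inference is by "using the appropriate contrast from the model to test the difference in CAPS score and PCL score between the two treatment arms" at each visit. No reference visit is named, but none is needed when contrasts are specified.
- **Primary time point.** "We plan an intent-to-treat analysis with the primary endpoint at 4 months". Response at 8 weeks is labelled early and response at 7 months sustained.
- **PCL scale.** The main-analysis paragraph calls the PCL "a continuous measure with a possible range of 17-85". Section 5.0 describes it as "a 20-item self-report measure of the DSM-5 symptoms of PTSD".

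**The concern.** Once group-by-time is in the model, the group coefficient is no longer a general arm effect. What it estimates depends on how time is coded, and the responder paragraph leaves that open. The PCL responder result could be an odds ratio at 8 weeks, 4 months or 7 months, or an average over visits. The choice would fall to the analyst or to a software default, and could be made after the data are seen.

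CAPS has no 8-week assessment, so a first-visit reference gives the two primary measures different time points under one and the same rule. The PCL responder result may then match neither the CAPS responder result nor the 4-month PCL contrast reported beside it.

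There is a smaller, separate point. The stated 17-85 range cannot belong to a 20-item scale. The 30% rule does not use the range, but a percentage reduction does depend on whether items are scored from 0 or from 1, and the item scoring is not given.

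**Working it through.** **1. The plan's own figures.** No figure is given for the responder analysis. The sample sizes used below come from the Sample size paragraph. A difference of 15.4, an SD of 28, 5% type I error (two-sided assumed) and 85% power give 60 per arm. Power at 60 is 85.4% by the normal approximation and 84.8% by the exact t-test. The design effect is 1 + (8 - 1) × 0.05 = 1.35, and 60 × 1.35 = 81 per arm. Then 162/0.70 = 231.4, which rounds up to 232. The stated total reproduces.

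**2. What the group coefficient means.** Let θ(v) be the log odds ratio between arms at visit v.

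| Time coding | PCL group coefficient | CAPS group coefficient |
|---|---|---|
| Indicator, first visit as reference | θ(8 wk) | θ(4 mo) |
| Indicator, 4 months as reference | θ(4 mo) | θ(4 mo) |
| Indicator, last visit as reference | θ(7 mo) | θ(7 mo) |
| Sum-to-zero | [θ(8 wk) + θ(4 mo) + θ(7 mo)]/3 | [θ(4 mo) + θ(7 mo)]/2 |

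Only the second row gives the plan's primary time point for both measures.

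**3. First illustration (rates assumed).** Control 25% at every visit; yoga 50% at 4 and 7 months; yoga 25%, 37.5% or 50% at 8 weeks.

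- Odds ratios from these rates: 25% v 25% = 1.0; 37.5% v 25% = 0.6/0.3333 = 1.8; 50% v 25% = 1/0.3333 = 3.0.
- Visit average, exp{[ln OR(8 wk) + 2 ln 3]/3}: 2.08, 2.53 and 3.0.

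These are marginal odds ratios. The mixed model estimates subject-specific ones, which are larger. With a random-intercept SD of 1 or 2, 1.8 becomes 2.01 or 2.57 and 3.0 becomes 3.72 or 5.95; 1.0 stays 1.0.

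Simulation: 600 datasets per scenario; three visits; logit model with group, time, group-by-time and a subject random intercept (SD 1 or 2, assumed); maximum likelihood with 15-point quadrature; two-sided 5% Wald test. Numbers per arm were 81, or 60 (81/1.35) as an approximation to class clustering, with no further dropout. Ranges span both sample sizes and both SDs.

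| Yoga responders at 8 weeks | 8 weeks as reference | 4 months as reference | Sum-to-zero |
|---|---|---|---|
| 25% | 4-7% | 78-92% | 67-89% |
| 37.5% | 27-39% | 78-92% | 88-99% |
| 50% | 80-92% | 78-92% | 97-100% |

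Entries are the chance that the PCL group coefficient is significant. A single-visit Wald calculation without random effects agrees. The standard error of the log odds ratio is √[1/(n p₁(1-p₁)) + 1/(n p₂(1-p₂))]. For 60 and 81 per arm, power is 5% at OR 1.0, 31% and 40% at OR 1.8, and 80% and 90% at OR 3.0.

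**4. Second illustration, with the effect fading by 7 months (rates assumed).** Control v yoga: 20% v 24% at 8 weeks, 25% v 45% at 4 months, 25% v 33% at 7 months. There are 81 per arm and fixed effects only, so the p-values ignore within-patient and class correlation.

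| Coding | PCL group OR (p) | CAPS group OR (p) |
|---|---|---|
| First visit as reference | 1.26 (0.54) | 2.45 (0.008) |
| 4 months as reference | 2.45 (0.008) | 2.45 (0.008) |
| Last visit as reference | 1.48 (0.26) | 1.48 (0.26) |
| Sum-to-zero | 1.66 (0.014) | 1.90 (0.008) |

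The data and the fitted model are the same in every row; only the coding differs.

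**5. PCL scoring.** 17 × 1 = 17 and 17 × 5 = 85, so the printed range fits 17 items scored 1-5. Twenty items give 0-80 if scored 0-4, or 20-100 if scored 1-5 (both scorings are assumptions). The same answers scored 40 on 0-80 need a fall of more than 0.30 × 40 = 12 points. Scored 60 on 20-100, they need more than 0.30 × 60 = 18.

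**The case against.** The strongest reply is that one interpretive sentence is being read too literally. The responder analysis is introduced as descriptive, and the preceding paragraphs set indicator-coded time, visit-specific contrasts and a 4-month primary endpoint. A statistician might well carry all of that over to a model with the same predictors. If indicator coding carries over, the sum-to-zero case drops out, but the reference visit is still unnamed. The contrasts are specified only for the continuous scores, and the responder paragraph then states a different rule, with a significance criterion. Following the text as written produces the problem.

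Other points stand as limits on its size:

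- The PCL/CAPS mismatch in visit needs a first-visit reference. A last-visit reference tests 7 months for both, so they agree but both miss the primary time point.
- The responder rates are assumed, and the starkest contrast takes no effect at 8 weeks and the full effect at 4 months. In that case 4-7% is the correct error rate for an 8-week test. What is wrong is the visit being tested.
- Every visit-specific odds ratio can be recovered from the fitted model.
- Aim 1 lists all three visits, so reporting all the visit-specific odds ratios would also remove the ambiguity. Giving 4 months precedence follows the plan's stated primary endpoint.
- The PCL range is a side issue and adds no weight to the main point.

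**Conclusion.** The concern holds. As written, the rule treats the group coefficient as an overall arm effect, which it is not in a model with group-by-time. Applied literally, it can test PCL at 8 weeks and CAPS at 4 months. The algebra needs no assumptions. How much the answer changes depends on assumed responder rates, on the random-intercept SD and on how early the effect appears, ranging from no discrepancy when the full effect is present by 8 weeks to the contrasts tabulated above. CAPS with a first-visit reference already tests 4 months; CAPS with a last-visit reference does not. The matter is confined to a secondary analysis, though one on both primary measures. It should be corrected.

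**What to change.** Replace the sentence on the group coefficient with wording such as: *The responder effect is the model contrast between arms at 4 months, reported as an odds ratio with 95% CI; contrasts at 8 weeks (PCL only) and 7 months are supportive.* The result then does not depend on how time is coded.

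As a minor correction, give the possible range of the 20-item PCL in the main-analysis paragraph, and state the item scoring on which the more-than-30% reduction is calculated.

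The cost is SAP wording only. The model, data collection and sample size do not change.

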5.0 Study Procedures

- Following informed consent and once a participant has been screened and meets inclusion criteria per the screening interview, a baseline assessment will be performed. The baseline assessment includes collection of sociodemographic data, substance use, psychiatric treatment utilization history, and assessments of PTSD (CAPS) and PTSD symptoms (self-reported PTSD symptoms, anger, sleep, anxiety, depression), and related outcomes (pain, well-being, quality of life, interoceptive awareness, and self-regulation). Substance use will be measured with 2 items. Alcohol use disorders will be assessed with the Alcohol Use Disorders Identification Test Consumption (AUDIT-C), which is commonly used in primary care settings, including VA primary care⁶⁶ and corresponds reasonably well with the full AUDIT⁹⁰. It can be scored continuously from 0 to 12, with higher scores representing riskier drinking, or categorically, with cutpoints of 3 for women and 4 for men having good sensitivity and specificity for hazardous drinking. Other substance use will be measured with the 10-item Drug Abuse Screening Test (DAST)⁹¹ which has shown to have good test-retest reliability, validity, and sensitivity, and specificity in detecting problem substance use⁶⁹.

See **Table 1** below for the administration schedule for all measures and time estimates for the assessment batteries.

Table 1. Outcome Assessment Protocol: Measures and Schedule of Administration

Domain	Measure	Items	Time (min)	Schedule				
				Screen	BL	8 wk FU	4 Mo FU	7 Mo FU
Demographics and Covariates	Screening Interview – Eligibility	22	10	X				
	Demographic/Covariate Form (BL/FU) AUDIT-C alcohol use DAST – drug use	21/12)	(7/3)		X	X	X	X
Overall PTSD Symptoms	CAPS – Clinician Interview	30	45	X			X	X
	PCL – Self Report	20	6		X	X	X	X
PTSD-Specific Symptoms	PROMIS Anger Short Form	5	2		X	X	X	X
	MOS – Sleep	12	3		X	X	X	X
PTSD-Related Outcomes	BDI – Depression	21	7		X	X	X	X
	STAI – Anxiety (state only)	20	5		X	X	X	X
	BPI – Pain	11	3		X	X	X	X
	SF-20 – Well-being/quality of life	20	6		X	X	X	X
Other Related Outcomes	MAIA - Interoceptive Awareness and /Self Regulation	32	10		X	X	X	X
	SCS-SF-Self compassion	12	3		X	X	X	X
	NGSES – self-efficacy	8	3		X	X	X	X
	Mental Illness Stigma	6	2		X	X	X	X
	FACIT-SP - spirituality	12	3		X	X	X	X
Treatment Factors	PPQ – Treatment Credibility	5	2		X			
	CSQ-8 – Client Satisfaction	9	3				X	
	Program Evaluation Questionnaire	10	8				X	

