
Treatment Factors will be assessed by three measures. The Pre-Program Questionnaire (PPQ)⁸¹ is an adaptation of Borkovec and Nau’s format⁸² and is a frequently used measure of treatment credibility. The questionnaire asks subjects to rate how confident they are in the program, how logical the program seems,

how successful they think it will be, how helpful the program leaders will be, and whether they would recommend the program to a friend, on a 10-point Likert-type scale. Treatment Satisfaction will be measured by the Client Satisfaction Questionnaire (CSQ-8), an 8-item scale that uses a 4-point likert scale to indicate participants' appraisal of their satisfaction with the intervention.⁸³ The CSQ-8 has excellent internal consistency, with a coefficient alpha of .87-.93, and evidence for the construct and concurrent validity of this measure has been reported as well.⁸⁴ A one-hour Program Evaluation Focus Group will be conducted with 15 randomly selected HYP participants to gather detailed information about participants' experience of the intervention to guide improvement of its structure and content. These participants will receive \$15 for completing the interview. [name], a sociologist experienced in qualitative methods, will train a member of the study staff to conduct the interviews, which will be audio recorded and transcribed. [name] will explore the data in order to understand participants' perceptions of the program, particularly in relation to PTSD, using Grounded Theory, an emergent constant comparative method.⁸⁹ The secondary analysis (Situational Analysis), will map all major features of participants' characteristics, perceptions, material elements and settings, in order to understand the relations and differences among them. All other participants will complete a brief program evaluation questionnaire with open-ended questions to ascertain likes and dislikes as well as suggestions for improvement of HYP or WLP. Treatment Engagement will be assessed by examining totals of treatment sessions attended and home practice completed.

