
Once baseline assessments are completed, the participant will be randomly assigned to the Holistic Yoga Program (HYP) or Wellness Lifestyle Program (WLP). The Holistic Yoga Program (HYP) arm will involve a standardized 16-week, yoga intervention consisting of: 1) a program orientation session conducted by a yoga instructor; 2) once weekly in-person group yoga class (postures, breathing practices, deep muscle contraction practices, relaxation practices) taught by a yoga instructor registered with Yoga Alliance at a minimum of the 200 hour level; 3) audio recordings of guided yoga postures, breathing, and relaxation practices for home-use; 3) a handbook to reinforce concepts taught during in-person session. Patients randomized to the Wellness Lifestyle Program (WLP) arm will participate in a standardized 16-week intervention that will consist of: 1) a program orientation conducted by a trained member of the study staff; 2) once weekly in-person group wellness classes (didactics and discussion of wellness topics and low intensity physical activity consisting of walking taught by a clinical psychologist with experience in trauma with consultation available from an experienced athletic trainer; 3) a handbook to reinforce wellness concepts and physical activity instructions taught during in-person session and to assist with home practice. After completing the program, participants will be asked to complete the same assessments as baseline with the addition of 2 program evaluation questionnaires. To minimize the potential for ascertainment bias, follow-up assessments (8 weeks, 4 months, 7 months) will be conducted by on-line survey and the interviews by a trained research assistant who will be blinded to treatment assignment. Participants will receive \$25 for completing the 8-week assessments, \$35 for completing the 16-week assessments and \$45 for completing the 7-month follow-up assessment. Those who fail screening will be given \$15.

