Sample size. Our sample size is calculated based on estimated differences of intervention effects between two arms on the primary outcome: CAPS total score at 4 months, or treatment end. The CAPS total score is a continuous measure (0-136) and reflects a combined score reflecting symptom frequency and symptom severity. A recently published yoga pilot study for patients with PTSD⁹ found a pre-treatment CAPS score of 77.33 (standard deviation = 28.6). Post-treatment scores were reduced by 34% (CAPS = 51.1, SD = 27.6, effect size = 0.9) from the yoga intervention. We powered on a medium effect size of 0.55 which requires a larger sample size than 0.9. We recognize the correlation of outcomes from subjects within the same yoga class may reduce the effective sample size compared to the same sample with independent observations. This possible “clustering effect” has implications for power. Randomization will occur at the individual not cluster or clinic level. Also, we expect that the intra-cluster correlation (ICC) will be near zero because groups will have a mixture of participants from the various recruitment sites: therefore, there is no reason to believe that participants within groups would be more correlated on the outcomes than participants from different groups. We have no preliminary data to estimate the intra-cluster correlation (ICC) for participants within the same group. However, based on similarly designed published studies, we expect the ICC to be relatively small and balanced across the two treatment arms since the cluster sizes will be similar. We will assume an ICC of 0.05 for both groups. We will also assume a 20% difference between treatment groups. The absolute score difference at 4 months is estimated to be approximately 15.4 points (61.6, 80% of 77). Assuming a common standard deviation of 28 and using a two-sample t-test, we will need 60 evaluable subjects in each arm to detect such a difference (Cohen’s $d = 0.55$) with >85% power and 5% Type I error rate. With approximately 8 subjects per treatment group/class session or cluster, the design effect is $1 + (8-1) \times 0.05 = 1.35$. Therefore, we will inflate our sample size by 35% to accommodate the potential clustering effects. We then need 81 evaluable subjects in each arm. With an assumed 30% attrition, we will then need $(81 \times 2) / 0.70 = 232$ subjects (116 in each arm).

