Analysis of secondary outcomes. Since RELIEVE is not specifically powered for secondary outcomes, these results should be interpreted cautiously unless they are highly significant ($p < .001$). PTSD-specific symptoms (anger, sleep) and PTSD-related symptoms/outcomes (well-being/QOL, depression, anxiety, pain) will be analyzed using the linear mixed modeling approach described above for the primary outcome. The secondary outcomes will be PTSD-specific symptoms including: anger (STAXI score), sleep (MOS score) and PTSD-related symptoms/outcomes: depression (BDI score), anxiety (STAI score), well-being/QOL (SF-12), and pain (BPI). Since there will be a number of secondary outcomes, we will adjust for multiple-comparisons by using the false discovery rate (FDR)⁸⁶ method to control the overall false positive rate at 0.05. Exploratory analyses of potential mediators/moderators: interoceptive awareness and self-regulation. Moderation effects will be assessed by testing two-way interactions between intervention group membership and demographic and baseline scales including treatment credibility, interoceptive awareness, self-regulation and type of trauma (combat vs non-combat related), mTBI. Mediation effects will be analyzed using the MPLUS structural equation modeling (SEM) software to test the direct, indirect, and total effects of paths in a multilevel SEM model that includes potential mediators measured at various study points (see table of measures) including client satisfaction, interoceptive awareness and self-regulation. Adherence to the interventions and home practice will also be assessed for its dose-response effects on the primary and secondary outcomes.

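### Client satisfaction is named as a mediator but is collected only at the 4-month endpoint visit, so the exploratory mediation model cannot tell cause from consequence for 4-month outcomes

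*Combined protocol and SAP*

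**What the plan says.** Section 8.0 (Analysis of secondary outcomes) plans a multilevel structural equation model that tests direct, indirect and total effects. The mediators are described as "potential mediators measured at various study points (see table of measures) including client satisfaction, interoceptive awareness and self-regulation". The run-in heading for this work is narrower: "Exploratory analyses of potential mediators/moderators: interoceptive awareness and self-regulation".

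The table of measures is the outcome assessment schedule in Section 5.0. Its row "CSQ-8 – Client Satisfaction" has one mark, under the 4-month follow-up. The text of Section 5.0 agrees: after the program, participants repeat the baseline battery "with the addition of 2 program evaluation questionnaires". The instrument records participants' "appraisal of their satisfaction with the intervention". Section 5.0 places it under Treatment Factors and leaves it out of the paragraph on potential mediators and moderators.

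The row "MAIA - Interoceptive Awareness and /Self Regulation" is marked at baseline, 8 weeks, 4 months and 7 months. Section 8.0 fixes the main assessment time as "4 months (the primary end point which occurs immediately post intervention".

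The plan does not say which outcome time the mediation model uses. It has no rule that the mediator must come before the outcome, and it does not mention adjusting the mediator path for concurrent or earlier symptoms.

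**The concern.** A mediation claim needs the mediator to act before the outcome. The CSQ-8 and the 4-month CAPS and PCL are taken at the same visit, after treatment has finished. Satisfaction with a program is a backward-looking judgement, and perceived improvement can plausibly shape it. A model with an arrow from satisfaction to symptoms fits the same covariance as one with the arrow reversed, so the data from that visit cannot choose between them.

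What is at stake is the interpretation of an indirect effect. A non-zero value could be read as a mechanism of the yoga program when part or all of it reflects participants who improved being more satisfied. A larger sample would not help, because this is bias and not sampling error.

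**Working it through.** **1. When is the CSQ-8 collected?** The minutes in the Section 5.0 table allow a check on the single mark.

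- Measures repeated at every visit from baseline on, without the demographic form: 6 + 2 + 3 + 7 + 5 + 3 + 6 + 10 + 3 + 3 + 2 + 3 = 53.
- 4 months: 3 (follow-up form) + 53 + 45 (CAPS) + 3 (CSQ-8) + 8 (program evaluation) = 112; stated 117.
- 7 months: 3 + 53 + 45 = 101; stated 106.

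Both stated totals are 5 minutes above the sum. The same 5 minutes appear at baseline (62 against 67) and at 8 weeks (56 against 61); the cause is not stated. The stated gap of 117 − 106 = 11 equals 3 + 8, so the CSQ-8 is counted at 4 months and not at 7.

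**2. The plan's effect size and numbers.** The sample-size paragraph says: "The absolute score difference at 4 months is estimated to be approximately 15.4 points". With SD 28, d = 15.4/28 = 0.55. A two-sided 5% test with 85% power needs 60 per arm. The design effect of 1.35 gives 60 × 1.35 = 81, and 162/0.70 = 231.4, rounded up to the stated 232. The concern does not depend on these figures; they only set the scale below.

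**3. Worst case for a 4-month outcome.** Let T be arm, Y the 4-month outcome and M satisfaction. Suppose satisfaction has no effect on Y and is caused by it:

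Y = τT + e, M = bY + u, with within-arm correlation r between M and Y.

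- Path from T to M: a = bτ.
- Within an arm, cov(M, Y) = b·var(e) and r² = b²·var(e)/var(M). The coefficient of M in a regression of Y on T and M is therefore b·var(e)/var(M) = r²/b.
- Indirect effect: bτ × r²/b = τr². The share of the total effect attributed to satisfaction is r², although the true share is zero.

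**4. Numbers.** The documents give no correlation between satisfaction and symptoms, so r is assumed. The last column comes from a simulation of this model with 81 per arm, d = 0.55 and 4,000 runs per setting. It has no clustering and takes mediation as declared when both paths are significant at 5%.

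| Assumed r | False share r² | Of 15.4 CAPS points | Both paths significant |
|---|---|---|---|
| 0.3 | 9% | 1.4 | 19% |
| 0.5 | 25% | 3.9 | 42% |
| 0.6 | 36% | 5.5 | 55% |

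The simulated shares match r².

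**5. The 7-month outcome.** Here satisfaction does come first. The 4-month symptom score can still drive both satisfaction and the 7-month score. With an assumed correlation of 0.7 between the 4- and 7-month scores, and no effect of satisfaction, leaving the 4-month score out gives the same false shares (9%, 25%, 36%), with both paths significant in 15%, 42% and 55% of runs. Putting it in brings the average satisfaction coefficient to about zero, significant in about 4–5% of runs. That removal is complete because the simulation makes the 4-month score the only common cause.

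**The case against.** The strongest reply is that the plan never says the mediation outcome is the 4-month score. Outcomes are also planned at 7 months, and the CSQ-8 precedes those. This stands: a valid time order exists for one outcome time, and a reader who inferred that satisfaction can never serve as a mediator here would go too far. The plan neither restricts satisfaction to that use nor adjusts for 4-month symptoms, so the gap remains.

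Second, reverse causation is plausible but not shown. Satisfaction may form during the 16 weeks and affect engagement. The documents give no evidence on direction, so they do not support saying that the indirect effect will be biased, only that the design cannot rule it out.

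Third, the r² figures are an extreme case: no effect of satisfaction at all, and all correlation running in reverse. Even then, at r = 0.5 or below, both paths reach significance in fewer than half of the simulated trials. These figures bound the problem under stated assumptions and do not estimate it.

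Fourth, the analysis is exploratory, its mediators are called potential, and its heading names only the two MAIA constructs. This limits the consequence. It does not supply the missing time order.

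Finally, time order alone is not enough for the MAIA mediators either. If 8-week symptoms influence 8-week MAIA and persist to 4 months, the same false path can appear. The fix below takes this in.

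**Conclusion.** The point holds in a limited form. Client satisfaction, collected only at 4 months, cannot support a mediation inference for a 4-month outcome, and the description of mediators measured at several study points does not fit it. The model can report an indirect effect where none exists, with a false share of up to r² of the treatment effect: 9% to 36% for assumed r from 0.3 to 0.6, if satisfaction has no effect and the whole correlation is reverse. For 7-month outcomes the weakness is confounding by 4-month symptoms, not reversed time order.

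A reader might infer that the trial will give a false account of how yoga works, or that its efficacy result is in doubt. The documents support neither. Satisfaction is one added variable in an exploratory model, and it is not named in the primary or secondary models. The point is minor, but it is more than missing detail, because a variable the plan names cannot do the job assigned to it at the primary endpoint.

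**What to change.** Change the mediation text in Section 8.0 as follows.

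- State the outcome time of each mediation model, and require the mediator to be measured before the outcome.
- Remove client satisfaction as a mediator of 4-month outcomes. Report it as a treatment factor, as Section 5.0 already classifies it.
- For 4-month outcomes, use the 8-week MAIA total and self-regulation scores, adjusted for baseline MAIA, the baseline outcome and the 8-week PCL. The PCL is the only PTSD severity score at 8 weeks, so in the CAPS model it is a proxy; say so.
- For 7-month outcomes, use 4-month mediators adjusted for the 4-month score of the same outcome.

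No new data are needed. The costs are one fewer mediator at 4 months and a narrower quantity: adjusting for the earlier symptom score excludes any mediated effect already expressed by that visit. The indirect effect is conservative in that sense and should be described that way.
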